8.1.4.3 Analysis on individual components of ASAS40

The change from Baseline in each individual component of the ASAS40 response (PGADA, total spinal pain score, BASFI, and BASDAI) will be analyzed at Week 16 using an analysis of covariance (ANCOVA) model. The analyses for the component variable BASFI will be described in Section 8.2.2 where analyses for secondary endpoints are described. For all four variables, the model will include treatment, prior TNF α inhibitor exposure and region as fixed effects and the respective Baseline values as covariate. These analyses will be done on the RS and will explore the effect of the signs and symptoms of the individual components on the composite endpoint.

The following 4 attributes describe the estimand that will be used to define the treatment effect of interest for each of the four components for this analysis:

- Population = Study participants enrolled according to the protocol-specified inclusion/exclusion criteria and randomized to IMP
- Study participant level outcome = The change from Baseline in the ASAS component variable at Week 16
- Intercurrent event handling = An intercurrent event is defined as discontinuation of study treatment due to any reason prior to Week 16. This estimand targets the treatment difference in a scenario where withdrawal from study treatment does not occur, such that outcomes for study participants without an IE are as observed, and outcomes for study participants with an IE are treated as they had completed the randomized study treatment through Week 16 but on placebo. In that strategy, missing data and non missing data after IE (reset as missing) will be imputed using reference-based MI, in which the MI model is based on data from the placebo group.
- Population-level summary measure = the difference in the adjusted means between bimekizumab and placebo.

Intermittent missing data will be imputed using the reference-based MI method as well. See Section 4.2.1.6 for technical details on how the reference-based MI method will be implemented.

The SAS[®] PROC MIXED will be used to run the ANCOVA model.

For each ANCOVA model specified in this analysis, the following statistics will be presented:

- a) For placebo and bimekizumab: the adjusted least-square means (LSM) and standard error (SE)
- b) For the comparison between placebo and bimekizumab: the difference between the LSM, the associated 95% confidence intervals for the contrasts, and the corresponding p-value.

An additional table will present the descriptive statistics for each ASAS40 component variable at Week 16. Those statistics will be the mean, SE, median, minimum and maximum obtained after MI.

The following supportive and additional analyses described in Section 8.1.4.4 to Section 8.1.4.8 are planned for the primary efficacy endpoint.

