8 EFFICACY ANALYSES

8.1 Statistical analysis of the primary efficacy variable

8.1.1 Derivation of ASAS40 response

The rules described in Section 4.2.1.1 will be followed in the derivation of the ASAS40 response. The ASAS40 response at Week 16 is the primary efficacy variable. The ASAS40 response is defined as:

- an improvement of at least 40%, and
- absolute improvement of at least 2 units on a 0 to 10 numeric rating scale (NRS) in at least 3 of the 4 following domains:
 - Patient's Global Assessment of Disease Activity (PGADA)
 - Pain assessment (total spinal pain, question 1 from total and nocturnal spinal pain)
 - Physical function (measured by the Bath Ankylosing Spondylitis Functional Index (BASFI))
 - Inflammation (represented by the mean of the Bath Ankylosing Spondylitis Disease Activity Index (BASDAI) questions 5 and 6) concerning morning stiffness intensity and duration)

- and no worsening at all in the remaining domain.

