8.1.1.2 Derivation of the pain assessment domain

The pain assessment domain will correspond to the total spinal pain and will be measured by the study participant in answering the following question “How much pain of your spine due to spondylitis do you have?”. To answer the question, the study participant will consider the average amount of pain in the preceding week and use a NRS ranging from 0 to 10, where 0 represents “no pain” and 10 represents “most severe pain”.

8.1.1.3 Derivation of the physical function domain of the Bath Ankylosing Spondylitis Functional Index (BASFI)

The BASFI contains 10 questions and will be measured by the study participant for assessing their physical functions during the past week. The first 8 questions evaluate activities related to functional anatomical limitations due to the course of AS. The final 2 questions evaluate the study participants’ ability to cope with everyday life. An NRS ranging from 0 (“Easy”) to 10 (“Impossible”) will be used to answer the questions on the test. The arithmetic mean of the 10 scores gives the BASFI score, which is a value between 0 and 10, with lower scores indicating better physical function.

In case of missing answers to 1 or 2 of the single items within the BASFI questionnaire, the BASFI score will be calculated by imputing missing items with the mean of the completed items. Then, the BASFI score will be calculated as described above. If more than 2 of the items are missing, the BASFI score will be left missing.

8.1.1.4 Derivation of the inflammation domain (mean of questions 5 and 6 of the BASDAI)

The BASDAI consists of 6 horizontal NRSs and will be used to measure the disease activity of ankylosing spondylitis from the study participant’s perspective. Each NRS contains 10 units to measure the severity of the 5 major symptoms: fatigue, spinal pain, peripheral joint pain and swelling, enthesitis, and morning stiffness (both severity and duration) over the last week.

The ASAS inflammation component is calculated as the average of the two scores relating to morning stiffness measurements (ie, question 5: “How would you describe the overall level of morning stiffness you have had from the time you wake up?” and question 6: “How long does your morning stiffness last from the time you wake up?”). The ASAS inflammation score ranges from 0 to 10.

If one of the two morning stiffness measurements is missing, the other one will be used as ASAS inflammation score.

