8.2.1.2 Bath Ankylosing Spondylitis Disease Activity Index (BASDAI)

As mentioned in Section 8.1.1.4, the BASDAI consists of six 10-unit NRSs measuring the disease activity of AS over the past week on 5 major symptoms. To give each symptom equal weighting, the average of the 2 scores relating to morning stiffness is taken. The BASDAI is calculated as follows:

$$BASDAI = \frac{Q1 + Q2 + Q3 + Q4 + \left(\frac{Q5 + Q6}{2} \right)}{5}$$

where Q1 – Q6 are the six questions from the BASDAI questionnaire.

The BASDAI score is between 0 and 10, with lower scores indicating lower disease activity.

As mentioned in Section 8.1.1.4, if 1 of the 2 morning stiffness measurements (ie, questions Q5 and Q6) is missing, the other one will be used for the morning stiffness calculation.

If one major symptom of the BASDAI is missing, the total score of the remaining symptoms will be divided by the number of symptoms assessed. If more than one major symptom is missing, the total BASDAI score will be set to missing.

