Subgroup analyses will also be conducted for ASDAS-MI endpoint using NRI. The variables of interest will be age, gender, race, region, ASDAS status and prior TNF α inhibitor exposure. Exact definition of the subgroups is provided in Table 4-4. The same methodology as the one used for the ASAS40 subgroup analyses will be followed. The results obtained for each subgroup will be combined in one single table as well as presented on a forest plot.

Finally, to assess the impact of the COVID-19 pandemic, the primary analysis of all secondary efficacy endpoints included in the testing hierarchy will be analyzed on the COVID-19 free set, using the Reference-Based Estimand.

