8.2.3 Additional statistical analysis of selected secondary efficacy variables

For the “change from Baseline in MASES index at Week 16 in the subgroup of study participants with enthesitis at Baseline”, and for the “enthesitis-free state at Week 16 based on the MASES Index in the subgroup of study participants with enthesitis at Baseline” secondary efficacy variables, additional statistical tests and calculation of inferential statistics will be performed. As these tests are not part of the multiplicity-controlled procedure, the associated p-values are considered nominal and are not controlled for multiplicity.

For the enthesitis-free state responder variable, the logistic regression model described in Section 8.1.2 will be used for analysis. The p-values will be based on the conditional logistic regression model to test general association. Missing values will be imputed using the NRI.

For the MASES continuous variable, the Hypothetical Estimand approach used for other continuous variables will be applied based on the ANCOVA model describe in Section 4.2.1.7 and Section 8.2.2.

The results of these inferential statistics will be presented in a single table summarizing the estimates (OR for the binary endpoint, LSM for the continuous endpoint) with their 95% CI and the associated p-values. The results will be pooled with the results obtained for selected other efficacy variables (see Section 8.3.3).

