For all these variables, the results based on the NRI will be combined with the ones obtained on OC and from the MI analysis in one single table.

In addition, a line plot by treatment group will be produced over time for some of the endpoints, that are part of the sequential testing procedure, based on NRI results, including the following binary variables: ASAS40 responder rate, ASAS40 responder rate in the TNF alpha inhibitor naïve study participants, ASAS20 responder rate, ASAS5/6 responder rate, ASAS-PR responder rate, and ASDAS-MI responder rate.

Continuous other efficacy variables that are components of the primary endpoint will be analyzed using the reference-based MI estimand and procedure described in Section 8.1.4.3.

For the continuous and categorical other efficacy variables (not including change from Baseline in WPAI-SHP, ASspiMRI-a (Berlin modification) score, and SPARCC score, and EQ-5D-3L Utility scores), the following estimand structure will be defined:

- Hypothetical Estimand (Section 4.2.1.7) – MI:
 - Population = Study participants enrolled according to the protocol-specified inclusion/exclusion criteria and randomized to IMP
 - Study participant-level outcome = The given variable and time point being summarized
 - Intercurrent event handling = An intercurrent event is defined as discontinuation of study treatment prior to the time point being summarized. This estimand targets the treatment difference in a scenario where the intercurrent event does not occur, such that outcomes for study participants without an intercurrent event are as observed at the given time point, and outcomes for study participants with an intercurrent event are treated as though they had completed the randomized study treatment through the time point being summarized
 - Population-level summary measure = Unadjusted mean.

The same imputation strategy for handling missing data as the one used for the secondary continuous efficacy endpoints as described in Section 8.2.2 will be implemented. Missing data for ASDAS status endpoint will also be imputed using MI, and the imputation will be done on the components of ASDAS-CRP prior to calculating ASDAS-CRP and categorizing ASDAS status. The mean proportion of responders in the multiply imputed data sets (with the associated 95% CI based on SE) will be displayed for each ASDAS category.

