8.3.3 Additional statistical analysis of selected other efficacy variables

Although statistical testing is not planned for other efficacy variables per protocol, statistical testing and inferential statistics are of interest for selected endpoints. As these tests are not part of the multiplicity-controlled procedure, the associated p-values are considered nominal and should not be used for inference. Similarly as described in Section 8.2.3, statistical tests and calculation of inferential statistics will be performed for the following selected other efficacy endpoints:

- ASAS40 at Week 1, Week 2, Week 4, Week 8, Week 12
- ASAS40 in the TNF alpha inhibitor-naïve study participants at Week 1, Week 2, Week 4, Week 8, Week 12
- ASAS20 at Week 1, Week 2, Week 4, Week 8, Week 12
- PGADA at Week 1, Week 2, Week 4, Week 8, Week 12, Week 16
- Total spinal pain at Week 1, Week 2, Week 4, Week 8, Week 12, Week 16
- Nocturnal spinal pain at Week 1, Week 2, Week 4, Week 8, Week 12
- BASFI at Week 1, Week 2, Week 4, Week 8, Week 12
- Mean BASDAI Q5 and Q6 score at Week 1, Week 2, Week 4, Week 8, Week 12, Week 16
- BASDAI at Week 1, Week 2, Week 4, Week 8, Week 12,
- BASDAI50 at Week 1, Week 2, Week 4, Week 8, Week 12, Week 16
- CRP at Week 1, Week 2, Week 4, Week 8, Week 12, Week 16
- ASDAS-CRP at Week 16
- MASES at Week 16
- Enthesitis free state at Week 16
- TJC at Week 16
- SJC at Week 16
- FACIT-Fatigue at Week 16
- WPAI at Week 16
- ASspiMRI at Week 16
- SPARCC at Week 16

The same models as described in Section 8.2.3 will be run, and results will be presented in one single table together with the results for secondary endpoints.

In addition, the Week 16 results from the primary analysis for the primary endpoint ASAS40, and key secondary endpoints in the hierarchy (ASAS20, BASDAI, BASFI, nocturnal spinal pain) will also be included in this table.

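### Three SAP passages on reference-based imputation need rewording: one covers binary endpoints (8.2.2, COVID-19 free set), one names BASDAI for its stiffness items (8.1.4.3), one leaves the component estimand open (8.3.3)

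*SAP*

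**What the plan says.** **COVID-19 free set.** The last paragraph of SAP Section 8.2.2 repeats the primary analysis of every secondary endpoint in the testing hierarchy; these "will be analyzed on the COVID-19 free set, using the Reference-Based Estimand". Earlier in the same section, NRI is set for the binary secondary endpoints, and the reference-based estimand is restricted to the continuous endpoints in the hierarchy.

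**Component analysis.** Section 8.1.4.3 covers "The change from Baseline in each individual component of the ASAS40 response (PGADA, total spinal pain score, BASFI, and BASDAI". Section 8.1.1 defines the fourth domain differently: "Inflammation (represented by the mean of the Bath Ankylosing Spondylitis Disease Activity Index (BASDAI) questions 5 and 6". Section 8.1.1.4 agrees: "The ASAS inflammation component is calculated as the average of the two scores relating to morning stiffness measurements".

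**Estimand for the components.** Section 8.3.2 says: "Continuous other efficacy variables that are components of the primary endpoint will be analyzed using the reference-based MI estimand". Section 3.10 declares the same choice as a change from the protocol, and footnote e of Table 4-1 reserves reference-based MI among the other continuous variables for these components. Section 8.3.3 then lists PGADA, total spinal pain and the question 5 and 6 mean at Weeks 1 to 16, and BASFI at Weeks 1 to 12, and says: "The same models as described in Section 8.2.3 will be run". For its continuous variable (MASES), Section 8.2.3 says that "the Hypothetical Estimand approach used for other continuous variables will be applied".

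**The concern.** In each passage the text names a variable or method that other sections contradict or leave open. On the COVID-19 free set, a continuous-outcome method is prescribed for binary endpoints, so the sensitivity analysis would not repeat the primary one it is meant to check. In the component analysis, the total score would stand in for the stiffness domain. In Section 8.3.3, PGADA and total spinal pain (and the question 5 and 6 mean, once 8.1.4.3 is corrected) could receive two Week 16 estimates and p-values under two estimands, with no statement of which one governs. The programming team would then have to settle these points after the plan is final.

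**Working it through.** This is a consistency check. No figure in the plan rests on these passages.

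**1. The plan's headline figure.** Section 2.4.1 states power above 99% for ASAS40. Inputs: 40% against 15%, 200 against 100, two-sided 0.05, continuity correction. With n = 100, r = 2, d = 0.25, the corrected size is n' = n[1 - (r+1)/(2rnd)]^2 = 100(1 - 0.03)^2 = 94.09. The pooled rate is (0.15 + 2 x 0.40)/3 = 0.3167. Then z = [0.25 x sqrt(2 x 94.09) - 1.96 x sqrt(3 x 0.3167 x 0.6833)] / sqrt(2 x 0.15 x 0.85 + 0.40 x 0.60) = (3.43 - 1.58)/0.704 = 2.63, which gives power of 99.6%. The figure reproduces, and nothing below enters it.

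**2. COVID-19 free set.** Section 2.4.2 lists these binary endpoints for the hierarchy: ASAS40 in TNF inhibitor-naive participants, ASAS20, ASAS-PR, ASDAS-MI and ASAS5/6. That makes five. In Table 4-1 the row for binary secondary endpoints in the testing procedure has NRI as primary method and no entry for reference-based MI. Section 4.2.1.6 imputes raw continuous values and finishes with an ANCOVA on change from Baseline; it has no step that derives or models a response. The rule in 8.2.2 therefore conflicts with its own section and with Table 4-1, and it cannot be carried out as written for these five endpoints.

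**3. Fourth component.** Sections 6.2.1, 8.1.1 and 8.1.1.4 all give the mean of questions 5 and 6. Section 8.2.1.2 introduces the total score ("The BASDAI is calculated as follows") as [Q1 + Q2 + Q3 + Q4 + (Q5 + Q6)/2]/5, so stiffness carries one fifth of its weight. Table 4-2 has a row for BASDAI and none for the question 5 and 6 mean, so it does not settle the matter.

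**4. Estimand in 8.3.3.** Sections 3.10, 8.1.4.3, 8.3.2 and Table 4-1 footnote e point to reference-based MI for the components. Section 8.3.3, through 8.2.3, points to the hypothetical estimand. The same table also receives the Week 16 primary-analysis results for BASFI, BASDAI total and nocturnal spinal pain, which are reference-based, beside the Week 1 to 12 rows.

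**5. Illustrative size.** The SAP gives no discontinuation rate. If a fraction f of bimekizumab participants has Week 16 imputed from the placebo model and loses the whole effect, a difference D becomes about D(1 - f). BASFI is the component with a planned difference, -2.35 (Section 2.4.2). For an assumed f of 3%: -2.35 x 0.97 = -2.28. For 15%: -2.35 x 0.85 = -2.00. The shift is 0.07 to 0.35 points. This is a rough guide and not a bound: f must also include intermittently missing values, which are imputed from the same model, and conditioning on each participant's earlier values may preserve part of the effect.

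**The case against.** **On 8.3.3** the defence is substantial. The text refers to the models of 8.2.3, which may mean only the logistic regression and the ANCOVA. It cannot import hypothetical MI for the whole list, because the list includes WPAI, ASspiMRI and SPARCC, for which footnote d of Table 4-1 rules out MI. Table 4-1 also marks both reference-based and hypothetical MI for other continuous variables, so running both is not forbidden. This stands: 8.3.3 is ambiguous, and a flat contradiction is not shown.

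A reader might also want BASDAI total and nocturnal spinal pain at Weeks 1 to 12 moved to reference-based MI, so that the time course uses one estimand. The SAP does not support that as a correction. Neither variable is an ASAS40 component, Table 4-1 gives them hypothetical MI at those visits, and the move would break footnote e.

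**On 8.1.4.3**, BASDAI is probably shorthand. The sentence speaks of the ASAS40 components, and only BASFI is redirected to 8.2.2, although BASDAI total is analysed there too. This supports the intention, but under the SAP's own definition the word still names the total score.

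**On the COVID-19 free set**, a programmer would probably default to NRI, since the sentence speaks of the primary analysis. That is likely, but the written instruction says otherwise.

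**Conclusion.** Two passages are wrong as written: the COVID-19 free set rule in 8.2.2 and the variable named in 8.1.4.3. The third, 8.3.3, needs clarifying. The analyses concerned are supportive or carry nominal p-values, and the primary analysis, the hierarchy tests and the power figures are untouched.

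Two stronger readings should be set aside. A reader might infer that the inflammation domain drops out of the analysis. It does not: the question 5 and 6 mean falls under the component rule in 8.3.2 and is tested up to Week 16 in 8.3.3.

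A reader might also infer that Week 16 will look visibly weaker than Week 12 because of the change of estimand. With an assumed 5% to 10% discontinuation, the BASDAI shift would be about 0.05 x 1.38 = 0.07 to 0.10 x 1.38 = 0.14 points, against a standard error of sqrt(1.8^2/200 + 1.4^2/100) = 0.19 from the planning SDs. The SAP states no such rate, and a visible step is not shown.

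**What to change.** - **Section 8.2.2, COVID-19 free set:** state that NRI is used for binary endpoints and reference-based MI for continuous endpoints.
- **Section 8.1.4.3:** replace BASDAI with the mean of BASDAI questions 5 and 6.
- **Section 8.3.3:** state that PGADA, total spinal pain, BASFI and the question 5 and 6 mean use reference-based MI at all listed visits up to Week 16. Leave BASDAI total and nocturnal spinal pain at Weeks 1 to 12 under hypothetical MI, as in Table 4-1. Label the estimand on each row of the combined table.

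The cost is three wording changes and a table label. Section 4.2.1.6 already imputes every visit in sequence up to Week 16, so the Week 1 to 12 ANCOVAs for the four components (4 variables x 5 visits = 20) need no further imputation method. If the total score was programmed literally for 8.1.4.3, the question 5 and 6 mean needs its own run of the same procedure.

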8.1.4.4 Analysis using modified composite estimand - MI

A supportive analysis will evaluate the modified composite estimand (Section 4.2.1.4.2) that combines the clinically meaningful improvement from Baseline in ASAS40 response at Week 16 and the intercurrent event of not discontinuing early from study treatment due to AE or lack of efficacy prior to Week 16.

The same logistic regression model as the one used for the primary efficacy analysis will be used on the RS. The following 4 attributes describe the estimand that will be used to define the treatment effect of interest for this analysis:

- Population = Study participants enrolled according to the protocol-specified inclusion/exclusion criteria and randomized to IMP
- Study participant-level outcome = ASAS40 at Week 16
- Intercurrent event handling = An intercurrent event is defined as discontinuation of study treatment due to AE (including death) or lack of efficacy, prior to Week 16. A composite strategy will be implemented in which a positive clinical outcome is defined as achieving ASAS40 at Week 16 and not discontinuing study treatment due to AE or lack of efficacy through Week 16.
- Population-level summary measure = Conditional odds ratio comparing bimekizumab to placebo.

Intercurrent events (Section 3.4) will be acknowledged as an unfavorable outcome for this modified composite estimand in considering study participants with intercurrent events as ‘non-responders’ to the study treatment.

Missing data at Week 16 that are not preceded by an intercurrent event will be imputed by standard MI techniques. Refer to Section 4.2.1.2 for further details.

8.1.4.5 Analysis using treatment policy strategy imputation for missing data

The treatment policy strategy will be investigated for addressing the intercurrent events. In this analysis, all available data at Week 16 will be considered regardless of the occurrence of intercurrent events. Missing data will be imputed by standard MI techniques. Refer to Section 4.2.1.9 for further details. This analysis will be based on the same logistic regression model as the one specified for the primary analysis where study participants are analyzed according to their randomized treatment even if they discontinued treatment prior to Week 16 and were no longer on the randomized study treatment when the assessment was performed at Week 16.

The following 4 attributes describe the estimand that will be used to define the treatment effect of interest for this analysis:

- Population = Study participants enrolled according to the protocol-specified inclusion/exclusion criteria and randomized to IMP
- Study participant-level outcome = ASAS40 at Week 16
- Intercurrent event handling = There are no intercurrent events defined for this estimand. Discontinuation of study medication for any reason will be handled by using the data as observed.

- Population-level summary measure = Conditional odds ratio comparing 'bimekizumab to 'placebo.

